Appendix 2: Screening logs

Screening activities will be carried out pursuant to 45 CFR 46.116(g) and 45 CFR 164.512(i). Patients in study hospitals will be entered into the screening log on the basis of an ordered COVID-19 test. Those who meet criteria for suspected or confirmed COVID-19 will be evaluated for all inclusion and all exclusion criteria. If all eligibility criteria are met, an informed consent conversation will occur. A HIPAA authorization waiver will be sought for this screening activity as per 45 CFR 164.512(i).

Appendix 3. Authorship criteria and management plan

After the conduct of the Main Study, the following policy will guide authorship decisions.

The ICMJE criteria for authorship will be followed. An author must make:

- Substantial contributions to the conception or design of the work; or the acquisition, analysis, or interpretation of data for the work; (a minimum of at least 2 of the above is needed) AND
- Drafting the work or revising it critically for important intellectual content; AND
- Final approval of the version to be published; AND
- Agreement to be accountable for all aspects of the work in ensuring that questions related to the accuracy or integrity of any part of the work are appropriately investigated and resolved.

Contributors who do not meet all 4 of these criteria for authorship will be listed as collaborators rather than authors.

For publications related to the Main Study (Main publications):

The overall PI will direct the authorship decisions for Main publications and will determine the following:

- Whether the results related to the aims are published as part of one manuscript or divided into multiple publications.
- To which journals the manuscript(s) will be submitted
- Any revisions and revision decisions for resubmission to journals for publication
- The order of authorship for the main publications in order of contribution as determined by the Protocol Committee according to the ICMJE recommendations within the following parameters:
 - The first and senior author should be members of the Protocol Committee. The first and senior author can make preliminary decisions about the scope of the manuscript, write the initial draft and decide on journal for submission and then present the plan to the rest of the Protocol Committee for approval.
 - All members of the Protocol Committee will be authors on the Main publications, as long as they meet ICMJE criteria.
 - Among Site PIs who contributed equally to the analysis and write-up of the Main publications, authorship order will be according to the number of patients recruited from the Site PI's site to the Main Study, with higher enrolling sites coming before lower enrolling sites.
 - If the journal limits the number of authors that can be listed, then the study will be attributed to the Protocol Committee and the Study Group, and the Site PIs and their sites will be listed in the acknowledgments, as collaborators, based on the number of patients enrolled from their site. In the event of ties, authorship order will be determined alphabetically, by site name.
 - Secondary site investigators from each site will not be included as authors unless they are on the protocol committee, but they will be listed as collaborators, based on the number of patients enrolled from their site. In the event of ties, authorship order will be determined alphabetically, by site name.

For publications of ancillary studies:

- Any Site Investigator or member of the Protocol Committee can propose an ancillary study to be considered by the Protocol Committee. The Protocol Committee must evaluate the proposal for appropriateness and overlap with other proposals.
- The ancillary study proposal should include the following:
 - Background or Rationale
 - Study Objective or Hypothesis
 - Proposed methods:
 - Study Design
 - Study Population

Hydroxychloroquine vs. Azithromycin for Hospitalized Patients with Suspected or Confirmed COVID-19 (HAHPS)

- Data Requested: List data needed for analysis of exposure, outcomes, and associated covariates.
- New Data or Intervention requested: List all data to be collected solely for the purpose of the proposed Ancillary Study.
- Proposed statistical approach
- Ancillary studies will be opened for other investigators to enlist as authors if they are interested. Lists of ancillary studies will be distributed periodically for review and sign up.
- The order of authorship will be decided by the investigator who proposed and leads the Ancillary Study, guided by the general principles outlined above and consistent with the ICMJE criteria.
- All abstracts and manuscripts from ancillary studies must be submitted to protocol committee for approval prior to submission.

Appendix 4.

As noted in section 7.2, investigators will report all adverse events that are serious and study drug or study procedure related to the DSMB. The DSMB and the PI will then notify the IRB.

The PI, in consultation with the DSMB, will determine whether a SAE has a reasonable possibility of having been caused by the study drug or procedure, as outlined in 21 CFR 312.32(a)(1). The PI, in consultation with the DSMB, will also determine whether the event is unexpected. An adverse is considered “unexpected” if it is not listed in the investigator brochure or the study protocol (21 CFR 312.32(a)). If a determination is made that a serious adverse event has a reasonable possibility of having been caused by the drug, it will be classified as a suspected adverse reaction. If the suspected adverse reaction is unexpected, it will be classified as a serious unexpected suspected adverse reaction (SUSAR).

The PI will report all unexpected and study related deaths, SAEs, and SUSARs to the DSMB within 24 hours of learning of the event. The PI and the DSMB will report their findings from review to the IRB within 7 days after report of the event to the DSMB. A final written report will be provided to the DSMB and IRB within 15 calendar days. The DSMB will also review all adverse events and clinical outcomes during scheduled interim analyses.

A4.1. UNANTICIPATED PROBLEMS (UP)

Investigators must also report Unanticipated Problems, regardless of severity, associated with the study drug or study procedures within 24 hours. An unanticipated problem is defined as follows: any incident, experience, or outcome that meets all of the following criteria:

- Unexpected, in terms of nature, severity, or frequency, given the research procedures that are described in the protocol-related documents, such as the IRB-approved research protocol and informed consent document; and the characteristics of the subject population being studied;
- Related or possibly related to participation in the research, in this guidance document, possibly related means there is a reasonable possibility that the incident, experience, or outcome may have been caused by the procedures involved in the research;
- Suggests that the research places subjects or others at a greater risk of harm (including physical, psychological, economic, or social harm) than was previously known or recognized.

A4.2. DETERMINING RELATIONSHIP OF ADVERSE EVENTS TO STUDY DRUG OR PROCEDURES

Investigators will grade the strength of the relationship of an adverse event to esmolol or study procedures as follows:

- Definitely Related: The event follows: (a) a reasonable, temporal sequence from study drug or a study procedure; and (b) cannot be explained by the known characteristics of the patient’s clinical state or other therapies; and (c) evaluation of the patient’s clinical state indicates to the investigator that the experience is definitely related to study procedures.
- Probably or Possibly Related: The event should be assessed following the same criteria for “Definitely Related”. If in the investigator’s opinion at least one or more of the criteria are not present, then “probably” or “possibly” associated should be selected.
- Probably Not Related: The event occurred while the patient was receiving esmolol or undergoing study procedures but can reasonably be explained by the known characteristics of the patient’s clinical state or other therapies.
- Definitely Not Related: The event is definitely produced by the patient’s clinical state or by other therapies administered to the patient.
- Uncertain Relationship: The event does not meet any of the criteria previously outlined.

[figure not shown]
A4.3. CLINICAL OUTCOMES THAT MAY BE EXEMPT FROM ADVERSE EVENT REPORTING

Study-specific clinical outcomes of COVID-19 or ARDS are exempt from adverse event reporting unless the investigator deems the event to be related to the administration of study drug or the conduct of study

procedures (or of uncertain relationship). The following are examples of events that will be considered study-specific clinical outcomes

- Death (unless Definitely or Probably related to study drug or procedures)
- Respiratory events: Changes in degree of hypoxemia or its treatment
- Cardiovascular events: changes in doses of vasoactive drugs; cardiac arrest; cardiac arrhythmias.
- Organ dysfunction events: changes in the SOFA score or its constituents.
- ICU admission
- Rash
- Hypoglycemia
- Seizure
- Elevations in ALT, AST, lipase, and amylase
- Acute Kidney injury and dialysis
- Cytopenias
- Nausea/vomiting
- Impaired vision
- *C. difficile* infection

A4.4. DECISION TREE FOR REPORTING ADVERSE EVENTS

Adapted from Ranieri VM, Thompson BT, Barie PS et al. Drotrecogin alfa (activated) in adults with septic shock. *N Engl J Med.* 2012 May 31;366 (22):2055-64. Epub 2012 May 22. PubMed PMID: 22616830 with permission of [name].

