After randomization, adverse events related to protocol procedures or occurring after the patient receives the first dose of study drug must be evaluated by the study investigator. If the adverse event is judged to be reportable, the investigator will report to the DSMB his/her assessment of the potential relatedness of each adverse event to study drug or study procedure. Investigators will assess whether there is a reasonable possibility that the study drug or procedure caused the event, based on the criteria outlined in Appendix 4. Investigators will also consider whether the event is unanticipated or unexplained given the patient's clinical course, previous medical conditions, and concomitant therapies.

Adverse events that will be collected prospectively as part of the study-specific outcome (and thus would not be separately reported as adverse events) are listed in Appendix 4. Study-specific outcomes will be reported as adverse events if they are both serious and Definitely or Possibly Related to study drug.

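### The adverse-event causality scale in Protocol A4.2 names esmolol, which is not a study drug, and its Definitely Related grade omits study drug from criterion (c)

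*Protocol*

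**What the plan says.** Section 7.1 of the Protocol puts the causality question in terms of the trial's own treatment: "Investigators will assess whether there is a reasonable possibility that the study drug or procedure caused the event". It tells the investigator to answer it "based on the criteria outlined in Appendix 4". The only graded scale in Appendix 4 is A4.2, headed "DETERMINING RELATIONSHIP OF ADVERSE EVENTS TO STUDY DRUG OR PROCEDURES".

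Under that heading the lead sentence is "Investigators will grade the strength of the relationship of an adverse event to esmolol or study procedures". Five grades follow. Two of them matter here:

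- **Definitely Related** has three criteria joined by and. Criterion (a) asks for "a reasonable, temporal sequence from study drug or a study procedure". Criterion (c) asks for a judgement that "the experience is definitely related to study procedures", with no mention of drug.
- **Probably Not Related** begins "The event occurred while the patient was receiving esmolol or undergoing study procedures" and goes on to require a reasonable explanation in the patient's condition or other therapies.

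Sections 5.2.1 and 5.2.2 give the study drugs as hydroxychloroquine and azithromycin. Esmolol appears nowhere else in either document.

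**The concern.** A4.2 is an operative safety rule, because other rules use its grades:

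- **Section 7.1:** nonserious events are collected if related or of uncertain relationship.
- **Section 7.2:** serious related events must reach the DSMB within 24 hours. After the first five days, serious events need reporting only if thought related.
- **A4.3:** listed outcomes are exempt from adverse-event reporting unless related or uncertain. The list includes arrhythmia, cardiac arrest, seizure, hypoglycemia and impaired vision. Several of these overlap with risks that section 5.4.1 gives for the study drugs.
- **SAP, Safety reporting:** a listed outcome becomes an adverse event if it is serious and related, or if it leads to permanent discontinuation. Adverse events are then compared between groups with nominal p-values.

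A scale that names another drug in its lead sentence and in one of its five grades, and omits drug from a criterion of the top grade, leaves investigators to infer what is meant. They may not all infer the same thing.

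**Working it through.** No figure in the Protocol or SAP depends on this point, so the check is a comparison of texts.

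**1. What each rule takes as the object of relatedness**

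| Place | Object |
|---|---|
| Section 7.1, collection rule and causality question | study drug or procedure |
| Section 7.2, DSMB alert | study drug or procedure |
| Appendix 4, PI and DSMB determination for serious events | study drug or procedure |
| A4.2 heading | study drug or procedures |
| A4.2 lead sentence | **esmolol** or procedures |
| Definitely Related (a) | study drug or procedure |
| Definitely Related (c) | **procedures only** |
| Probably Not Related | **esmolol** or procedures |
| A4.3 exemption | study drug or procedures |

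Three places depart from the rest, all within A4.2.

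**2. Esmolol in Probably Not Related, read literally.** Take a participant on hydroxychloroquine whose event is reasonably, but not definitely, explained by the illness. The event fits this grade only if it occurred on esmolol or during a study procedure. If neither applies, it may fall to Uncertain Relationship. There a nonserious event is collected under section 7.1, and a listed outcome loses its A4.3 exemption. This error leans towards more reporting.

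**3. Criterion (c), read literally.** Take an event caused by drug alone. It can meet (a) and (b) but not (c), so Definitely Related is closed to it. An event that misses a criterion goes to the combined Probably or Possibly grade, and the scale gives no rule for choosing between the two words.

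**4. Where step 3 matters most.** The A4.3 entry for death lifts the exemption only for the Definitely and Probably grades. A drug-caused death shut out of Definitely is therefore reportable under that entry if called Probably and exempt if called Possibly. Section 7.1 uses a different pair, Definitely and Possibly, for serious study-specific outcomes. The two passages disagree on the very words on which the event now turns.

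**5. What does not depend on the grade**

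- Section 7.2 collects serious events in the first five days whatever the presumed cause. The listed A4.3 outcomes have their own exemption rule, counted above as exposed.
- Section 7.1 collects events leading to permanent discontinuation whatever the grade, and the SAP counts them on that ground alone.
- SAP Table 2 lists 21 safety outcomes. Only death unrelated to treatment or procedures is defined by causality, so 21 − 1 = 20 are not.

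**The case against.** The strongest reply is that this is an obvious leftover word. The governing question in section 7.1, the heading of A4.2, criterion (a), the alert rule, the determination for serious events and A4.3 all say study drug, and an investigator would read past the slip. For serious events, the PI with the DSMB separately judges causality against the study drug. An event that fails (c) is still graded as related, and an event pushed to Uncertain Relationship is more likely to be recorded, not less.

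Most of this stands, and it rules out several stronger readings that a reader might infer:

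- **That the plan does not ask about relatedness to hydroxychloroquine or azithromycin.** It does, in the places listed above. A4.2 contradicts that rule; it does not replace it.
- **That no participant receives esmolol.** The documents show only that it is not a study drug. It is not among the exclusions or the Appendix 5 medications, and its clinical use is not prohibited.
- **That the comparison between arms is biased.** The wording is the same for both arms. The trial is open-label, which makes a clear scale more desirable, but the documents show no mechanism by which this wording would act differently by arm.
- **That the case report forms carry the error.** The CRF guidance is not in the documents.

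The reply does not answer criterion (c). It names no foreign drug that would alert the reader. Taken at face value, it closes the top grade to drug-caused events, with the consequence for deaths in step 4.

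**Conclusion.** A4.2 is wrong as written in three places and should be corrected. It contradicts its own heading and the rest of the Protocol.

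The exposure is limited to the collection of nonserious events, serious-event reporting after day 5, the 24-hour DSMB alert, the A4.3 exemptions (the entry for death above all) and the SAP's count of serious related events. The effect on event counts cannot be computed from the documents, and no bias between arms is shown.

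The conclusion assumes that investigators apply A4.2 as printed, at least in part. If all of them read study drug throughout, the practical effect is nil. Two points cannot be settled from the available text. The A4.4 decision tree is a figure that is not shown, so the route from grade to report cannot be fully traced. The SAP also does not say whether a Table 2 outcome that is reclassified as an adverse event stays in the Table 2 count; the statement that 20 of 21 rows are unaffected assumes that it does.

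**What to change.** In A4.2, replace esmolol with study drug (hydroxychloroquine or azithromycin) in the lead sentence and in Probably Not Related. End criterion (c) of Definitely Related with study drug or study procedures. In the same amendment, reconcile the grades named in the A4.3 entry for death with those named in section 7.1.

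Check whether any form or guidance derived from A4.2 carried the wording over, and correct it only if it did. The SAP describes interim analyses as already performed, so events may already have been graded. Check whether any of those grades were affected, starting with deaths and serious events after day 5.

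The cost is one amendment with three wording changes in A4.2, the reconciled grade wording, and a limited review of graded events. Design, sample size and analysis do not change.

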Official Title: Hydroxychloroquine vs. Azithromycin for Hospitalized Patients With Suspected or Confirmed COVID-19 (HAHPS): A Prospective Pragmatic Trial

NCT #: NCT04329832

Document Date: Jun 29 2020

Responsible analytic personnel

[name]
Professor of Medicine and Epidemiology
University of Utah

[name], MStat
Biostatistician, Intermountain Medical Center

[name]
Biostatistician, Intermountain Medical Center

Responsible investigators

[name]
Associate Professor of Medicine
Intermountain Medical Center/University of Utah

[name], DO
Physician investigator
Intermountain Medical Center

[name]
Professor of Medicine
University of Utah

[name]
Assistant Professor of Medicine
Intermountain Medical Center

Table of Contents

BACKGROUND	2
SUMMARY OF ANALYTIC APPROACH	3
General	3
Analysis Sets	3
Primary Analysis	4
Secondary Analyses	7
Sub-groups	8
Missing Data	8
Safety reporting	9
Concomitant medications	11
Interim Monitoring	12
Sample size and power	12

Background

The HAHPS trial is a randomized, open label, active comparator trial of hydroxychloroquine vs. azithromycin for hospitalized patients with COVID-19. The HAHPS trial enrolled patients admitted to the hospital with suspected or confirmed COVID-19. As outlined in the protocol and a prior publication,¹ the eligibility criteria excluded patients with markers of increased risk associated with administration of hydroxychloroquine or azithromycin. The trial is being conducted at Intermountain and University of Utah hospitals. While the trial is open-label, outcomes assessors and investigators are blinded to outcomes by treatment group. This SAP was written by blinded personnel, without knowledge of study outcomes.

Summary of analytic approach

General. Descriptive summaries will be produced for subject disposition, demographic and clinical characteristics of the randomized hydroxychloroquine and azithromycin groups. The primary analysis and other secondary analyses of efficacy outcomes will be performed in accordance with the intention-to-treat (ITT) principle, with all patients analyzed according to their randomized treatment assignment, irrespective of compliance. In addition to the formal statistical analyses described below, the proportions of subjects with each level of the 8-point COVID scale will be displayed in frequency tables and in graphical summaries for each day, from day 0 (baseline) through day 14 of follow-up. Other ordinal secondary outcomes will generally be summarized using medians, 10th, 25th, 75th, and 90th percentiles and plots of cumulative distribution functions. In cases where a substantial proportion of subjects fall into an extreme category, several of the indicated quantiles may take on the value of this category and a quantile-based summary may not be fully informative. In these cases, we will tabulate the proportions of subjects which fall into designated categories which are defined based on clinical relevance.

Adherence to the study medications will be summarized by providing the distributions of the proportion of doses of study medication which were administered to each patient overall and by randomized group. We will compute two proportions: 1) The proportion of protocol-intended dose, in which doses for which the patient had a protocol-specified reason not to receive study medication (e.g., prolonged QTc, died, or discharged home) will not be counted in the denominator for proportion of scheduled doses received. 2) The proportion of the total ideal dose, in which doses for which the patient had a protocol-specified reason not to receive study medication will be counted. We will also describe the median (IQR) for total doses received for both protocol-intended dose and ideal dose.

Analysis Sets. The primary analysis and analyses of secondary efficacy outcomes will be performed in the ITT population, which consists of all randomized patients. Although the trial was launched with the flexibility to enroll patients with suspected rather than confirmed COVID-19, no patients were HAHPS SAP

actually enrolled under that criterion. The ITT population thus simplifies to patients with laboratory-confirmed COVID-19. Summaries of safety outcomes will be performed in the safety population consisting of all patients who receive at least one dose of study medication. In a subgroup of the ITT population, we will compare study endpoints among patients who had not received azithromycin before randomization.

Primary Analysis. The prespecified primary analysis will compare the day 14 assessment of the 8-level COVID Ordinal Outcomes Scale between the randomized hydroxychloroquine and azithromycin groups. We will perform this analysis using a proportional odds logistic regression model (also called an ordinal regression model),² with randomized treatment group as the independent variable. Patient age, comorbidities (dichotomized as either no comorbidities or any comorbidities, with the comorbidities drawn from hypertension, COPD, and the Charlson constituent comorbidities³ (Table 1), and the baseline level of the COVID Ordinal Outcomes Scale will be included in the analysis as covariates. Due to restriction of the cohort to hospitalized patients, the baseline COVID Ordinal Outcomes Scale distribution will include only patients with levels 3 through 7. In a sensitivity analysis, we will include the total amount of pre-randomization azithromycin received as another covariate in the primary model.

Table 1. Charlson Comorbidities

Moderate/Severe Liver Disease
Cerebrovascular Disease (CVD)
Peripheral Vascular Disease (surgical)†
Renal disease
Peripheral Vascular Disease (diagnosis) †
Paralysis (Hemiplegia or Paraplegia)
Dementia

Mild liver disease
Congestive heart failure (CHF)
Chronic Obstructive Pulmonary Disease (COPD)
Diabetes with complications
Diabetes

Under the ordinal regression model, the treatment effect is expressed as the odds ratio comparing the odds of patients having a score that exceeds a given threshold vs. a score that is less than or equal to that threshold, and those odds are compared between the hydroxychloroquine and azithromycin groups. An odds ratio less than 1 thus represents treatment benefit for hydroxychloroquine over azithromycin. The model assumes that this odds ratio is the same across all possible thresholds across the 8-level ordinal scale. However, the primary analysis using the proportional odds model is closely linked to the Wilcoxon-rank-sums test and is thus expected to provide approximately valid inference even if the proportional odds assumption is violated.⁴ Nonetheless, we will graphically assess the compatibility of the data with the proportional odds assumption by running a series of binary logistic regressions with varying cutpoints on the dependent variable and visually checking the deviation of coefficients across cutpoints. If the proportional odds assumption is clearly violated, our primary analysis under the proportional odds model will be supplemented with separate odds ratios comparing different groups of categories for which the proportional odds assumption is violated.

Following a structure proposed by Harrell and collaborators (<http://hbiostat.org/proj/covid19/bayesplan.html>), the primary analysis will be performed using a Bayesian framework, with a conservative normal prior distribution assumed for the log transformed odds ratio. The normal prior will be assigned a mean of 0 (thus taking an agnostic position as to the direction of the treatment effect), and a standard deviation of 0.354. This prior distribution assigns a probability of 0.95 to an odds ratio between 0.5 and 2.0, with a probability of 0.025 that the odds ratio HAHPS SAP

is below 0.50 and also a probability of 0.025 that the odds ratio is greater than 2.0. The use of this moderately conservative Bayesian prior will tend to shrink the observed proportional odds ratio towards 0, and thus moderately discount extreme observed odds ratios which may occur particularly for early interim analyses with relatively small sample size.

The results of the Bayesian analysis will be expressed as (1) a graphical display of the posterior distribution of the odds ratio, (2) the posterior mean, median and mode with 95% credible intervals, and (3) the following probabilities of clinical relevance based on the posterior distribution of the odds ratio (OR) given the data:

$P1 = \Pr(\text{OR} < 1)$, indicating the evidence for any benefit of hydroxychloroquine over azithromycin;

$P2 = \Pr(\text{OR} < 1/1.25)$, indicating the evidence for a moderate benefit or greater of hydroxychloroquine over azithromycin;

$P3 = \Pr(\text{OR} > 1)$, indicating the evidence for any harm of hydroxychloroquine over azithromycin;

$P4 = \Pr(\text{OR} > 1.25)$, indicating the evidence for a moderate harm or greater of hydroxychloroquine over azithromycin;

$P5 = \Pr(1/1.2 < \text{OR} < 1.2)$, indicating the evidence for similarity between the two treatments.

For the purposes of primary inference, we will employ the 95% posterior probability of $P1$ or $P3$ as evidence for either benefit or harm of hydroxychloroquine over azithromycin. Evidence for moderate harm of hydroxychloroquine ($P4$) would be considered to be demonstrated at a lower 75% posterior probability threshold. In any case, the distributions of $P1$ – $P5$ will be displayed for reference in the statistical report of the primary analysis. For clarity and simplicity, posterior Bayesian probabilities will be estimated by applying a normal approximation to the maximum likelihood estimate of the proportional odds ratio obtained by fitting the likelihood function to the data. This simplification will

avoid the complication of specifying prior distributions for the intercept coefficients in the proportional odds model.

Secondary Analyses. We will apply similar Bayesian proportional odds models to evaluate the effectiveness of the hydroxychloroquine vs. azithromycin interventions for efficacy analyses of all ordinal outcomes. We will also present numbers (proportions) of patients in each ordinal status for all endpoints for descriptive purposes and to assist with future meta analyses. If the graphical diagnostics (described above) indicate that the proportional odds model is untenable for certain outcomes, we will report that fact, and supplement the primary analysis using the proportional odds model with separate logistic regression for different cutpoints or quantile regression in order to fully characterize the relationship of each outcome with treatment assignment.

Ordinal secondary outcomes include ventilator-, ICU-, and hospital-free days through day 28 (with death assigned as a worst-rank ordinal level^{5,6} to avoid survivorship bias for each of these outcomes). We will use the last-off method—only time after the last liberation from, e.g., ventilation counts toward the total number of -free days. Similar to the primary outcome measured at 14 days, we will apply a primary proportional odds model similar to that used for the primary analysis at day 14 to evaluate the effect of the randomized treatments on the COVID Ordinal Outcomes Scale at day 7. We will present the results of each of these analyses as the posterior median odds ratio with 95% credible interval under the moderately skeptical Bayesian prior described above. For ease of use for investigators performing meta-analyses, we will include detailed descriptions including number of patients for each value of the endpoints by treatment group as tables in the online supplement.

We include two time-to-event endpoints, censored at 28 days: time to a 1-point decrease in the COVID Ordinal scale and time to recovery (defined as in the ACTT-1 trial). The time to recovery endpoint was added after publication of the methods paper but before unblinding of investigators. It was added to assist with future meta analyses given increasing interest in it as an endpoint. Both time-to-event endpoints will be displayed by treatment group (for descriptive purposes) as Kaplan-HAHPs SAP

Meier curves. Patients who die prior to day 28 are assigned an artificial follow-up time of 28 days censored at that point. This will assign to these patients a worse outcome than any surviving patients, and avoid conflating prolonged hospitalization with death. Descriptively, these time-to-event endpoints will be displayed as median (IQR). If fewer than half of patients meet the event before censoring, we will choose an appropriate quantile (e.g., first quartile) for description and display the proportions with events during the respective weeks of follow-up. For the sake of consistency, we will use the same ordinal regression model with the same prior distribution for the odds ratio as was used for the primary analysis to generate median posterior odds ratios and credible intervals for these endpoints.

Sub-groups. On a purely exploratory level, we will summarize effect variation in sub-groups defined by (a) age \geq 65 years, (b) symptom duration \geq 10 days, (c) in ICU at enrollment, (d) presence of at least one comorbidity, (e) race/ethnicity, and (f) receipt of any clinical azithromycin before enrollment. At early interim analyses, the sample size will be too small to support meaningful statistical inference, and we will limit presentation of results in sub-groups to descriptive summaries using the summary measures described for each outcome above.

Missing Data. We expect fewer than 5% of subjects will have missing data on either the primary or key secondary outcomes listed above. Hence, our primary analyses will be restricted to non-missing observations, without imputation. For the primary outcome, a sensitivity analysis will be performed by applying single imputation. Where daily COVID Ordinal Outcomes Scale scores are missing after hospital discharge, we will use last carried forward with the following modifications—patients discharged to a facility other than home will be classified as “home with limitations” (score 2), and patients found subsequently to be home with limitations will be rated as “home with limitations” from hospital discharge through that follow-up point. Patients who are discharged to home and found to have no limitations at day 14 will be rated as “home without” limitations starting at the time of hospital HAHPS SAP

discharge. This approach will be used because persisting limitations are unlikely to have resolved and then recurred by 14 days. Similar single imputation rules will be devised for sensitivity analyses of secondary efficacy endpoints consistent with prior practice in the field and will be determined before the given analysis is performed to avoid bias from knowledge of outcomes.

Safety reporting

The HAHPs trial uses the adverse event reporting developed for the PROWESS-SHOCK trial.^{7,8} This approach is based on the high incidence of conditions resulting from the underlying disease that would be classified as adverse events if they occurred in healthy outpatients but are unlikely to be related to the study drug. Instead of being classified as adverse events, such events are monitored as study clinical or safety outcomes (Table 2). The exception to this rule are events which are either serious and study-related or which lead to permanent discontinuation of study drug. Those latter are reported as adverse events and are classified within the MedDRA taxonomy.

For reporting purposes, for each safety outcome or adverse event each patient will be classified as having experienced the outcome at least once (vs. never having experienced the outcome). We will separately provide counts (proportions) of safety outcomes and individual adverse events. In early interim analyses, comparisons of safety outcomes between treatment groups will be viewed as primarily descriptive. However, we will provide nominal p-values to compare adverse events and safety outcomes between groups without multiple comparison adjustment using the Chi square or Fisher exact test as appropriate to provide a crude assessment of the compatibility of observed differences between treatment groups with chance. Isolated p-values which are < 0.05 will be interpreted recognizing that 5% of such p-values will reach this threshold by chance in the absence of an actual effect of the treatment.

QTc was monitored at 24–48h after randomization as a study procedure. QTc monitoring at baseline was not mandatory but was described where it was available. We also described the change between baseline and 24–48h after randomization in QTc. These results will be summarized HAHPs SAP

descriptively by treatment group. If the baseline QTc is available in at least 80% of participants, an analysis of covariance will be performed to compare follow-up QTc between treatment groups with adjustment for baseline QTc. Otherwise, a 2-sample t-test will be used to compare the follow-up QTc levels.

Table 2 Safety outcomes (measured daily for first five days)
Death unrelated to study drug or procedures
Seizure
Receipt of vasopressors
Atrial or ventricular arrhythmia
Cardiomyopathy
cardiac arrest
Hypoxemia requiring supplemental oxygen
ARDS
Mechanical ventilation
ECMO
Elevated LFTs
Pancreatitis
Acute kidney injury
Renal replacement therapy
Symptomatic hypoglycemia
Hematologic or coagulation events
Cytopenias
Severe dermatologic reaction

Nausea/vomiting
Visual changes
C. diff infection

Concomitant medications

The classes of concomitant medications listed in Table 3 were measured at baseline (before randomization) and through day 5 after randomization. Concomitant medications will be descriptively summarized overall and by treatment group. In addition, some patients in the hydroxychloroquine arm received azithromycin either before or in some cases after randomization. The proportion receiving azithromycin was recorded, and in exploratory summaries, safety outcomes will be displayed in that group as well as in the groups who received only azithromycin or only hydroxychloroquine.

Table 3. Concomitant medications
ACE inhibitors
ARBs
NSAIDs
Glucocorticoids
Immune-suppression
Chloroquine
Hydroxychloroquine
Azithromycin
Zinc
Vitamin C

Interim Monitoring.

Under the Bayesian design, the posterior distribution describing the accumulating evidence provided by the data for treatment benefit or harm was updated at successive interim analyses during the trial.⁹ After consultation with the DSMB and consistent with the DSMB charter written before the first interim analysis, we performed interim analyses after enrollment of every 60 patients. This cadence for interim analyses was confirmed through simulation to yield performance characteristics consistent with a trial-wise alpha of approximately 0.05 if a frequentist approach had been taken.¹⁰ We adopted a Bayesian approach to allow the DSMB to recommend continuation or closure of the trial based on the totality of evidence, including data from the present trial and from other relevant experiments or trials. While the trial is not designed to be stopped for futility based on the trial data alone, the DSMB is authorized to incorporate the totality of evidence in making decisions about recommending closure of the trial to further enrollment.

Sample size and power. We generated an approximate sample size and power calculation by providing the odds ratios closest to 1 (corresponding to the minimum detectable treatment effects, which are indicated by odds ratios less than 1, reflecting treatment benefit for hydroxychloroquine over azithromycin) which can be detected in a frequentist analysis of the primary outcome under a proportional model without covariate adjustment. The target sample size of this trial is 300 randomized subjects; Table 4 also considers smaller sample sizes to indicate the power the trial will reach under various scenarios for enrollment depending on state-wide disease dynamics. The power calculations were performed using statistical simulation (N=10,000 simulations per combination of parameters), and provide results very close to those provided by an approximation provided by Whitehead.¹¹ For the sample size calculation, we considered three scenarios for the distribution in the azithromycin group for the 8 categories of the COVID Ordinal Outcomes Scale: Scenario 1: Uniform distribution with probabilities of 0.125 for each score level, Scenario 2: Overall probabilities at 14 days HAHPS SAP

averaging across both groups of the recent COVID-19 trial by Cao et al.¹² (1= 0, 2= 0.36, 3=0.16, 4=0.23, 5=0.05, 6=0.02, 7=0.02, 8=0.16), and Scenario 3, with probabilities averaged between Scenarios 1 and 2.

